9.7.5. Sensitivity analyses

Sensitivity analyses will be conducted:

- to only include patients in areas covered by the mortality surveillance system and with higher completeness on survival data.
- to only include patients before COVID-19 emergence (cohort identification period: January 1, 2013 December 31, 2019) to assess the possible impact of COVID-19 pandemic on treatment patterns and outcomes.

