9.2.3. Study visits

Definitions of relevant time periods are detailed below.

Study period: January 1, 2013 – December 31, 2022

Baseline period: All available data prior to index date

[figure not shown]
Cohort identification period: January 1, 2013 – December 31, 2021 (one year before end of study period)

Index date: The index date for Cohort 1 will set to the date of initiation of 1L treatment; the index date for Cohort 2 will be the date of initial DDLPS diagnosis during cohort identification period.

Follow-up period: From index date until date of death, if available, or the date of censoring if there is no record of death, whichever occurs first. For survival and treatment patterns, the date of censoring will be the last activity date, defined as the date of the last visit of any type prior to the end of the study period.

Figure 1 illustrates the time periods for the study timelines.

(a). Cohort 1

NIS Protocol BI Study Number 1403-0024

Page 14 of 37 C42272174

Proprietary confidential information© 2023 Boehringer Ingelheim GmbH or one or more of its affiliated companies (b). Cohort 2

[figure not shown]

Figure 1. Overall study period

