9.3.1. Outcomes

9.3.1.1. Primary outcomes

OS

Outcome type: Primary

Outcome name: OS

• **Time frame:** Time from index date until the earliest record of death or end of the study period

Population: Cohort 1

OS as an event for each patient in Cohort 1 will be defined as the date of death minus the index date or the start day of each LOT. For patients with no record of death, OS will be censored at the last activity date before the end of the study period.

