9.5. STUDY SIZE

The patient sample was a convenience population of all eligible patients in the database who met inclusion and exclusion criteria during the study period; no priori power analyses were conducted.

NIS Protocol BI Study Number 1403-0024 Page 22 of 37 C42272174

Proprietary confidential information© 2023 Boehringer Ingelheim GmbH or one or more of its affiliated companies

A preliminary feasibility check will be conducted to assess potential eligible sample size as below.

Criteria
Patients with at least one diagnosis of DDLPS
Patients aged 18 years old or above at initial diagnosis
Patients have two or more documented clinical visits between January 1, 2013 and December 31, 2022

We estimated the precision we can expect from the estimates of a median OS for different potential sample sizes. It is assumed that the enrollment rates follow uniform distribution in the study period and that the survival time follows exponential distribution with median OS=8, 10, and 12 months. The censor rate is approximately 20% with type I of right censoring. The 95% CI of median OS is shown in the below table under different scenarios.

N (Sample Size)	Median Overall Survival from start of 1L, Months	95% CI of Median Overall Survival
1500	8	(7.419, 8.625)
1000	8	(7.287, 8.764)
500	8	(7.011, 9.095)
300	8	(6.732, 9.435)
1500	10	(9.262, 10.784)
1000	10	(9.100, 10.972)
500	10	(8.754, 11.378)
300	10	(8.408, 11.814)
1500	12	(11.110, 12.948)
1000	12	(10.916, 13.175)
500	12	(10.491, 13.677)
300	12	(10.073, 14.198)

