9.7. DATA ANALYSIS

The statistical analysis plan for the study is summarized below. Full details of the statistical analysis will be documented in the Statistical and Epidemiological Analysis Plan (SEAP), which will be finalized before the end of data collection.

This study will be descriptive in nature.

It is anticipated that sample sizes for variables may vary due to unknown or missing data in the database. The number of patients with missing data for each variable will be summarized and reported. With the exception of the imputation of partial missing date values, no other imputation of missing values will be undertaken; however, the impact of missing data on interpretation of findings will be acknowledged and discussed in the final study report.

For all analyses, data for patients will be censored when lost to follow-up (i.e., still alive as of their last visit prior to end of study period).

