10.1 MAIN ANALYSIS

10.1.1 Analysis of primary objective

OS will be analyzed for Cohort 1. For OS calculation, the event time is the date of death recorded by the National Mortality Database from CDC. OS is defined as the time from initiation of 1L until the date of death due to any cause. Patients without death record during the study period will be censored at the last medical record during the study period.

OS will be estimated by the KM method to obtain median estimates with 95% CIs and IQRs for Cohort 1, calculated using the log-log transformation. OS rate at 6, 12, 18, and 24 months will be described according to the survival curves if reached.

OS may be assessed by LOT and type of treatment received in each LOT, pending feasibility. OS by LOT is defined as the time from initiation of each LOT until the date of death due to any cause.

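### The COVID-19 sensitivity analysis restricts index dates to 2019 but, on the readable text, keeps follow-up to 2022, so pandemic-era follow-up is reduced rather than removed (minor).

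*Protocol*

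**What the plan says.** Protocol 9.7.5, like the abstract, describes an analysis "to only include patients before COVID-19 emergence" and gives the window in parentheses: cohort identification from January 2013 to the end of 2019. The purpose is "to assess the possible impact of COVID-19 pandemic on treatment patterns and outcomes". Neither place gives this analysis its own end of follow-up.

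The readable follow-up rules all point to the end of the study period, 31 December 2022:

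- Protocol 9.7 (repeated in SAP 10) is general: "For all analyses, data for patients will be censored when lost to follow-up", with loss judged at the last visit before the study period ends.
- Protocol 9.2.3 censors survival and treatment patterns at the last activity date, "defined as the date of the last visit of any type prior to the end of the study period".
- Protocol 9.3.1.1: "OS will be censored at the last activity date before the end of the study period".
- SAP 10.1.1: "Patients without death record during the study period will be censored at the last medical record during the study period".

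In the main analysis, identification ends on 31 December 2021, "one year before end of study period".

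**The concern.** The pandemic acts in calendar time. Protocol 9.9 itself describes restricted access to oncology services and fewer hospital visits, which would reach a patient indexed in 2019 and still in care in 2020 as well as one indexed in 2020. A filter on index date removes the second patient but leaves the first patient's pandemic-era follow-up in the result.

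A programmer working from the readable text would therefore keep 2020-2022 events in the restricted analysis. Any pandemic effect on outcomes would then be somewhat diluted in the comparison with the main analysis, and a reader could take the result as free of pandemic exposure. SAP Annex 2 replicates the output tables for sensitivity analyses where feasible. Numbers of lines, resource use and cost also accumulate over follow-up, so the point is not confined to OS.

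**Working it through.** **Inputs.** Time is in months from 1 January 2013.

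- Restricted window ends at month 84 (Protocol 9.7.5); main window at month 108 and study period at month 120 (Protocol 9.2.3).
- Uniform entry and exponential survival with median m = 8, 10 or 12 months (Protocol 9.5). I spread index dates evenly over the identification window.
- Censoring (Protocol 9.5): "The censor rate is approximately 20% with type I of right censoring".
- The 80% death capture in Protocol 9.9 cancels from the shares if it is constant over time.

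**The plan's own figure.** Simulated exponential survival with about 20% censoring and a log-log Kaplan-Meier interval (400 runs per scenario) gives (8.74, 11.39) for N = 500 and median 10. Protocol 9.5 states (8.754, 11.378). All 12 stated intervals are matched to within about 1.2%, so the planning assumptions are read correctly.

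**Deaths per 1,000 main-analysis patients, no loss to follow-up.** With λ = ln 2 / m:

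- A, indexed by 2019 and dying in 2020-2022: (1000/108) × (1/λ)(1 − e^(−84λ))(1 − e^(−36λ))
- B, indexed in 2020-2021 and dying by the end of 2022: (1000/108) × [24 − (1/λ)(e^(−12λ) − e^(−36λ))]
- C, all deaths in patients indexed by 2019: (1000/108) × [84 − (1/λ)(e^(−36λ) − e^(−120λ))]

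At m = 10, 1/λ = 14.427:

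- A = 9.259 × 14.427 × 0.9970 × 0.9175 = 122.2
- B = 9.259 × (24 − 14.427 × 0.3528) = 175.1
- C = 9.259 × (84 − 14.427 × 0.0822) = 766.8

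The pandemic-era share is (A + B)/(B + C) in the main analysis and A/C in the restricted one. The count falls by B/(A + B).

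| m | A | B | C | Main share | Restricted share | Fall in count |
|---|---|---|---|---|---|---|
| 8 | 102.1 | 189.2 | 773.1 | 30.3% | 13.2% | 65% |
| 10 | 122.2 | 175.1 | 766.8 | 31.6% | 15.9% | 59% |
| 12 | 139.2 | 162.1 | 757.9 | 32.7% | 18.4% | 54% |

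**With about 20% censoring.** Add random loss at 0.25λ: replace λ by 1.25λ in the formulas and multiply by 0.8. This censors 20-21% of the restricted cohort. Main shares become 29.1/30.3/31.3%, restricted shares 10.8/13.2/15.4%, and the count falls by 71/65/60%.

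**Other accrual.** With accrual growing 10% a year (an assumption) and no loss, the ratio of restricted to main share is 0.43/0.49/0.54, against 0.44/0.51/0.56 under uniform accrual.

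**Effect on the median.** Suppose the death hazard is multiplied by k from January 2020. The values of k are assumed; the documents give none. Kaplan-Meier medians in months by numerical integration, for main / as planned / follow-up also cut at 2019:

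| m | k = 1.25 | k = 1.5 | k = 2.0 |
|---|---|---|---|
| 8 | 7.54 / 7.91 / 8.00 | 7.18 / 7.84 / 8.00 | 6.63 / 7.71 / 8.00 |
| 10 | 9.41 / 9.86 / 10.00 | 8.94 / 9.74 / 10.00 | 8.24 / 9.55 / 10.00 |
| 12 | 11.27 / 11.80 / 12.00 | 10.69 / 11.64 / 12.00 | 9.83 / 11.36 / 12.00 |

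The fraction of the contrast shown is (planned − main)/(cut − main). At m = 10, k = 1.5 this is (9.74 − 8.94)/(10.00 − 8.94), about 76%. Over the grid it runs from about 71% to 81%, leaving 0.1 to 0.6 months unseen. Random loss does not change these medians.

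**The case against.** The strongest reply is that nothing is mislabelled. Protocol 9.7.5 states its window openly and restricts which patients enter; it does not promise pandemic-free follow-up. Restricting by index date is a legitimate design choice, and it deals directly with the fall in diagnoses that Protocol 9.9 describes. This stands. A reader might infer that the plan contradicts itself, but the readable follow-up rules agree with one another and the documents do not support that reading.

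A second reply is that Protocol 9.7 sends full analytical detail to the SAP, where section 10.2 is not available for review and could hold a follow-up rule. This also stands. It would be wrong to infer that the plan as a whole lacks a cut-off; what can be said is that Protocol 9.7.5 is silent on one.

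A third is importance. The planned run shows most of the contrast. The largest unseen difference, 0.6 months, needs a 12-month median and a doubled hazard throughout 2020-2022. For about 233 patients (300 × 84/108) the 95% interval for median OS is itself 3.1 to 4.6 months wide at medians 8 to 12. That fixes the point as minor. It does not remove the case for one inexpensive extra run, given the stated aim of assessing outcomes.

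**Conclusion.** The point holds as a minor, inexpensive improvement to Protocol 9.7.5. As readable, the analysis reduces pandemic-era follow-up without removing it: about 11 to 18% of its Cohort 1 deaths would still fall in 2020-2022, against 29 to 33% in the main analysis. A reader might conclude that pandemic-era deaths are merely halved. That roughly describes the share; the count falls by 54-65% without loss and 60-71% with about 20% censoring.

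Nor do the documents support a claim that the primary OS estimate is compromised, since this analysis does not feed into it.

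The shares rest on uniform accrual over 2013-2021 and exponential survival with median 8 to 12 months; actual accrual is not given. The effect on the median rests further on assumed hazard multipliers. The documents give no rates with which to size the effect on treatment lines, visits or costs.

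**What to change.** Keep the planned analysis unchanged and label it *indexed before COVID-19, follow-up to 2022*. Add a second version to Protocol 9.7.5, and to the SAP unless the section not available for review already contains it:

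*Patients alive on 31 December 2019 are censored at their last activity on or before that date. Later deaths, treatment lines, visits and costs are not counted. Cohort membership and resectability status use data up to that date.*

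Report both versions beside the main analysis.

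The cost is one label, a short paragraph and one extra run. The statistical price falls on the added version only:

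- Entry and follow-up end on the same day, so the one-year minimum potential follow-up is lost; under uniform accrual 12/84 = 14% of patients have less than 12 months.
- Cohort 1 deaths fall by A/C, 13-18% without loss, or about 11-16% with about 20% censoring, depending on how the loss is set.
- With about 233 patients and about 20% censoring, the mean 95% interval for median OS widens from 3.1 to 3.2, 3.9 to 4.0 and 4.6 to 4.9 months at medians 8, 10 and 12 (1,500 simulated data sets).

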9.2.2. Study population

Inclusion criteria:

- Patient has two or more documented clinical visits in the National Anti-Tumor Drug Surveillance System (NATDSS) network on or after January 1, 2013.
- Patient has a confirmed diagnosis of DDLPS during his/her lifetime.
- At least 18 years old at the date of initial diagnosis

No exclusion criteria are applied.

Eligible population will be divided into two groups:

NIS Protocol BI Study Number 1403-0024

Page 13 of 37 C42272174

Proprietary confidential information© 2023 Boehringer Ingelheim GmbH or one or more of its affiliated companies

- Cohort 1 will include unresectable locally advanced or metastatic DDLPS patients who received at least one line of systemic antineoplastic treatment by the end of cohort identification period (index date = start date of 1L treatment).
- Cohort 2 will include patients with DDLPS who have not initiated 1L systemic antineoplastic treatment by the end of cohort identification period (index date = date of initial DDLPS diagnosis during cohort identification period). Patients initiated 1L treatment afterwards or patients received adjuvant and/or neoadjuvant therapy only through follow-up will be included in Cohort 2.

In both cohorts, 1L therapy will be defined as the initial set of drugs used after unresectable locally advanced or metastatic diagnosis. Metastatic patients will be defined as those with metastatic diagnosis or presence of metastatic sites; unresectable locally advanced patients will be defined as those with advanced diagnosis and without subsequent surgical resection.

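### The COVID-19 sensitivity analysis moves the date that sorts patients into cohorts, so Cohort 2 changes with no pandemic effect, while Cohort 1 is set against a group that contains it

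*Protocol*

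**What the plan says.** Protocol 9.2.2 (repeated in SAP 6.3) sorts patients by one date. Cohort 1 holds unresectable locally advanced or metastatic patients "who received at least one line of systemic antineoplastic treatment by the end of cohort identification period". Cohort 2 holds those "who have not initiated 1L systemic antineoplastic treatment by the end of cohort identification period", and the rule adds: "Patients initiated 1L treatment afterwards or patients received adjuvant and/or neoadjuvant therapy only through follow-up will be included in Cohort 2". A Cohort 2 patient is indexed at initial diagnosis, which must fall inside the identification period.

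Protocol 9.2.3 fixes the dates for the main analysis: "Cohort identification period: January 1, 2013 – December 31, 2021 (one year before end of study period") and "Study period: January 1, 2013 – December 31, 2022".

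Protocol 9.7.5 then plans an analysis "to only include patients before COVID-19 emergence (cohort identification period: January 1, 2013 December 31, 2019"), with the aim "to assess the possible impact of COVID-19 pandemic on treatment patterns and outcomes". The abstract says the same. Neither place gives a different end of study period or says whether main-analysis cohort labels are kept.

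Survival after initial diagnosis and treatment patterns are secondary outcomes for both cohorts (Protocol 9.3.1.2), and treatment is counted during follow-up. SAP Annex 2 intends the tables for both cohorts to be repeated for the sensitivity analyses where feasible.

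**The concern.** The sensitivity analysis resets the very term that defines the cohorts. Read literally, it does more than remove recent patients: it changes the cohort of some who remain. It also lengthens the time in which a Cohort 2 member can start 1L before the study period ends, from one year (2022) to three (2020-2022). A change in Cohort 2's treated share or survival could then be reported as a pandemic effect when it comes from the cohort rule.

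Cohort 1 has a different weakness. The contrast on offer is 2013-2019 against 2013-2021, and the second set contains the first, so a real difference is diluted.

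**Working it through.** **Step 1. Who moves.** Apply the 9.2.2 rule to patients who start 1L in 2020-2021. All are Cohort 1 in the main analysis.

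| Initial diagnosis | Period ends 31 Dec 2021 | Period ends 31 Dec 2019 |
|---|---|---|
| 2013-2019 | Cohort 1 | Cohort 2 (1L not yet started, diagnosis inside the period) |
| 2020-2021 | Cohort 1 | in neither cohort (no 1L start and no diagnosis inside the period) |

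Cohort 1 loses patients and gains none; it becomes the 1L starts up to the end of 2019.

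**Step 2. Size in Cohort 2, with no pandemic effect built in.** The plan states no figure to reproduce. The size depends on the share of patients who ever start 1L and on the gap from diagnosis to 1L, and the documents give neither. Two sets of assumptions were simulated. Both use exponential times and follow-up to 31 Dec 2022.

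*Set A: patients may die before 1L.* Diagnosis is uniform over 2013-2021 and median survival after 1L is 10 months (a value used in Protocol 9.5). The other inputs are assumptions.

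| Ever 1L | Median gap (months) | Median survival without 1L (months) | Cohort 2 share with 1L: main | Sensitivity |
|---|---|---|---|---|
| 40% | 18 | 60 | 3.4% | 7.9% |
| 40% | 12 | 60 | 3.5% | 7.2% |
| 50% | 24 | 60 | 4.3% | 10.5% |
| 30% | 18 | 80 | 2.6% | 6.1% |

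In these four rows moved patients make up 5-8.5% of the sensitivity Cohort 2, and its median survival after diagnosis falls by about 2-4 months (first row: 52.0 to 49.6). With a 3-month gap the effect shrinks: the 1L share goes from 2.2% to 2.9%, moved patients are about 3%, and the median falls about 1.4 months. Repeat runs differ by about 0.2 month.

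*Set B: everyone destined for 1L receives it.* Diagnosis is uniform over 2013-2022 (the accrual shape in Protocol 9.5), OS from 1L has a median of 8 or 12 months (also 9.5), and median survival without 1L is 48 months (assumed). Nobody is lost to follow-up. Five of the twelve scenarios:

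| Ever 1L / gap / OS from 1L (months) | 2020-2021 starters who move | Moved, as share of sensitivity Cohort 2 | 1L share: main, sensitivity, kept labels | Median survival (months): main, sensitivity, kept labels |
|---|---|---|---|---|
| 30% / 3 / 12 | 17.9% | 2.1% | 1.6%, 2.1%, 0.0% | 47.9, 47.1, 48.2 |
| 30% / 12 / 8 | 53.9% | 6.0% | 3.2%, 7.0%, 1.1% | 49.0, 46.9, 48.8 |
| 60% / 3 / 8 | 17.8% | 7.1% | 5.3%, 7.1%, 0.0% | 46.8, 43.6, 48.1 |
| 60% / 12 / 8 | 53.7% | 17.5% | 9.6%, 20.5%, 3.6% | 51.8, 45.7, 51.7 |
| 60% / 24 / 8 | 70.4% | 18.1% | 9.2%, 23.3%, 6.5% | 64.7, 57.6, 64.0 |

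Over all twelve, 18-71% of the 2020-2021 starters move and the rest drop out. The median falls by 0.8 (47.9 - 47.1) to 7.1 months (64.7 - 57.6). In both sets the 1L share rises and the median falls in every scenario.

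**Step 3. Would keeping the main labels remove the shift?** Here Cohort 2 keeps its label from 31 Dec 2021 and is restricted to diagnosis by 31 Dec 2019. In Set B its median then stays within about 1.3 months of the main Cohort 2 (largest gap shown: 48.1 - 46.8 = 1.3). The 1L share, however, now falls, to 0.0-6.5%, because only 2022 starters diagnosed at least two years earlier remain. Set A agrees: in a repeat run of its first row the share goes from 3.5% to 1.4%.

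**Step 4. Dilution in Cohort 1.** Let p be a proportion fixed at index (say, the share on one 1L regimen) in 2013-2019, and q the same in 2020-2021. With even accrual over nine index years, the main analysis shows (7/9)p + (2/9)q. Main minus sensitivity is (7/9)p + (2/9)q - p = (2/9)(q - p). A 10-point difference appears as 10 x 2/9 = 2.2 points.

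**The case against.** The restriction to patients before COVID-19 can be read as a simple filter on index date with labels kept. The public SAP text goes from 10.1.2 to 10.3, so section 10.2 cannot be checked and may say exactly that. This stands: the point concerns what the visible wording produces, and it cannot be counted as a proven omission.

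A reader might infer that every patient starting 1L in 2020-2021 is relabelled. The Cohort 2 index rule excludes those diagnosed in 2020-2021, and with a 3-month gap they are the large majority of such starters (about 82% in Set B). A reader might also infer that the primary outcome is biased. OS is a Cohort 1 outcome, and Cohort 1 is only restricted.

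Keeping the main labels has its own fault. Membership then depends on whether 1L began in 2020-2021, so a pandemic delay in 1L would itself change the labels, and the 1L share is pushed down (Step 3). The literal rule at least assigns labels on information up to 2019. This stands too, and it limits what kept labels can be used for.

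Finally, leaving out a period and comparing with the full set is a common form of sensitivity analysis. Year of initial diagnosis is a possible subgroup (Protocol 9.7.4) and index year is tabulated (SAP Annex 2, Table 1). But that subgroup is optional, is defined by diagnosis and not by 1L start, and is not tied to the pandemic question. The 2/9 factor holds for proportions fixed at index under even accrual. It does not carry over to Kaplan-Meier medians, and patients indexed by 2019 are still followed into 2020-2022.

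**Conclusion.** The concern holds for Cohort 2 as the visible text is written. Patients diagnosed in 2013-2019 who start 1L in 2020-2021 change cohort, the window for 1L starts grows from one year to three, and both the treated share and survival after diagnosis shift with no pandemic effect. The direction is the same in every scenario tried. The size is not established: about 3-8.5% of the sensitivity Cohort 2 and a fall of about 1.4-4 months in the median under Set A, and 2-18% and 0.8-7.1 months under Set B. It is small if 1L soon follows diagnosis and few patients are treated.

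Cohort 1 OS is not distorted by relabelling. The Cohort 1 weakness is the overlapping comparison, which shows a difference in a proportion fixed at index at about 2/9 of its size under even accrual. The effect is confined to a sensitivity analysis in a descriptive study, but that analysis cannot isolate what it sets out to assess.

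**What to change.** In Protocol 9.7.5 and the matching SAP text:

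1. **Cohort 1.** Report patients indexed in 2013-2019 and in 2020-2021 side by side, and judge pandemic impact on that contrast. No relabelling is involved and the two groups do not overlap.
2. **Cohort 2, survival after diagnosis.** State that the main-analysis label (1L status at 31 Dec 2021) is kept and that the restriction is diagnosis by 31 Dec 2019.
3. **Cohort 2, share with 1L.** State that a change in this share is not read as a pandemic effect under either labelling. The literal rule lengthens the window after the cut-off; kept labels leave only 2022 starters.

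If SAP section 10.2 already fixes the labels, the Protocol needs only a sentence to match.

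The cost is some wording and one extra column. The 2020-2021 group is small, so its intervals will be wide. Kept labels still depend on what happened in 2020-2021, and the report should say so.
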